7.2 Laboratory Tests

We will be using test results from standard of care lab for the study. These test results include, antibody profile (antiphospholipid antibodies, ENA).

If these blood tests never have been performed, they should be done as routine blood tests. Women will have a blood test including full blood count, kidney and liver function at screening (available pre-trial results from within 3 months can be used for study purposes) and every three months once they have started the IMP to ensure the monitoring of potential adverse side effects caused by hydroxychloroquine. If the rare event occurred that women develop abnormal creatinine clearance of 30ml/min women will be withdrawn from the trial.

Laboratory tests for selected sites:

Women will be invited to donate 15 ml of blood at baseline, at the first pre-pregnancy visit, once every trimester and post partum (max 6 weeks post partum). Only women recruited in Denmark will be invited to donate 17,5 ml of blood (as pax-gene tube will be included) at baseline, at the first pre-pregnancy visit, once every trimester and post partum (max 6 weeks post partum). Specimens will be analyzed for HCQ levels (pharmacokinetics) and biomarker studies. Where possible the blood collection will coincide with routine blood tests and study bloods will be kept locally in established laboratories. A research team member will personally transport the bloods to the laboratory. Blood samples can be handled in room temperature. These studies will be undertaken on separate funding. A log will be kept for the blood samples. This log will be signed be the research team member transporting the blood samples to the laboratory.

8 Assessment of Efficacy

8.1.1 Primary Efficacy Parameters

The primary efficacy parameters will include the absence of pregnancy complications, i.e. as defined in the primary endpoint is defined as follows:

The primary endpoint is a composite of three principal aPL-related adverse pregnancy outcomes: one or more pregnancy loss(es) (either < 10 weeks gestation or beyond 10 weeks of gestation of a morphologically normal fetus documented by ultrasound or by direct examination of the fetus) and premature birth of a morphologically normal neonate before 34 weeks due to any of: pre-eclampsia, eclampsia, recognized features of placental insufficiency Premature birth for other reasons will not be included.

The components of the primary endpoint will each be presented as secondary endpoints (below).

The pre-defined secondary endpoints include:

- 1. Pregnancy loss < 10 weeks gestation
- Pregnancy loss > 10th weeks of gestation of a morphologically normal fetus documented by ultrasound or by direct examination of the fetus
- 3. Premature birth of a morphologically normal neonate < 34 weeks due to any of: pre-eclampsia, eclampsia, recognized features of placental insufficiency.
- 4. Gestational age at delivery
- 5. Birth weight
- 6. Delivery by Caesarean section
- 7. Apgar score < 7 at 5 min
- 8. Neonatal morbidity (bleeding or thrombotic complications, infections, congenital abnormalities)
- 9. Days to hospital discharge following delivery (mother & child)
- 10. Thrombotic events in the mother during pregnancy and 6 weeks post-partum.
- 11. Days of neonate in special care
- 12. Safety and tolerability of hydroxychloroquine in the mother and in the neonate

The components of the primary endpoint will each be presented as secondary endpoints.

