4.1.1 Primary endpoints

The primary endpoint is a composite of three principal aPL-related adverse pregnancy outcomes: one or more miscarriage (either < 10 weeks gestation or between 10 and 27+6 weeks gestation) and premature birth before 34 weeks due to any of: pre-eclampsia, eclampsia, fetal growth restriction (FGR) or stillbirth (i.e. after 24 weeks).

Premature birth for other reasons will not be included.

The components of the primary endpoint will each be presented as secondary endpoints (below).

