4.1.2 Secondary endpoints

The pre-defined secondary endpoints include:

The pre-defined secondary endpoints include:

- 1. Pregnancy loss < 10 weeks gestation
- 2. Pregnancy loss > 10th week of gestation of a morphologically normal fetus documented by ultrasound or by direct examination of the fetus
- 3. Premature birth of a morphologically normal neonate < 34 weeks due to any of: pre-eclampsia, eclampsia, recognized features of placental insufficiency.
- 4. Gestational age at delivery
- 5. Birth weight
- 6. Delivery by Caesarean section
- 7. Apgar score < 7 at 5 min
- 8. Neonatal morbidity (bleeding or thrombotic complications, infections, congenital abnormalities)
- 9. Days to hospital discharge following delivery (mother & child)
- 10. Thrombotic events in the mother during pregnancy and 6 weeks post-partum.
- 11. Days of neonate in special care
- 12. Safety and tolerability of hydroxychloroquine in the mother and in the neonate

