5.3 IMP Risks

Hydroxychloroquine is traditionally an antimalarial drug and since the 1950's has been widely used in the treatment of patients with rheumatoid arthritis or systemic lupus erythematosus (SLE). Hydroxychloroquine treatment of pregnant patients with SLE was first described more than three decades ago and its safety during pregnancy has been extensively documented and systematically reviewed [5-7].

The European Medicines Agency has licensed hydroxychloroquine as orphan medical product for the treatment of APS (EU/3/16/1820). We are aware that hydroxychloroquine is labelled as 'contraindicated in pregnancy' according to the SmPC. However, it is widely used in women during pregnancy and lactation and is recommended for the use in pregnancy by European and British Societies (the European League against Rheumatism (EULAR) and the British Society for Rheumatology (BSR)).

[name] is a member of the BSR working group on 'prescribing antirheumatic drugs in pregnancy'. Their guidance has been published in *Rheumatology* [9, 44]. After reviewing more than 810 pregnancies in the literature where women were prescribed hydroxychloroquine through pregnancy, they recommended that hydroxychloroquine is the antimalarial drug of choice in pregnant patients with autoimmune diseases and they did not identify significant risks for intrauterine exposure to the fetus. According to these NICE approved BSR guidelines, hydroxychloroquine is the antimalarial of choice for pregnant patients requiring immune modulation [9, 44]. The BSR guideline has been updated in November 2022, as hydroxychloroquine is still the antimalarial of choice for pregnant women and deemed safe before conception, during pregnancy and also during breastfeeding [45, 46]. Safety assessments for mother or baby are not recommended.

Further supporting the safety of hydroxychloroquine in pregnancy and lactation, the EULAR have very recently published their European recommendations on the use of hydroxychloroquine in pregnancy and lactation. The EULAR group highlighted that hydroxychloroquine is safe in pregnancy and that there is no evidence of an increased risk of malformations in children exposed to hydroxychloroquine, that hydroxychloroquine can be continued throughout pregnancy and during breastfeeding [47].

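### Malformed fetuses lost after 10 weeks are missing from the malformation endpoint and score as non-events on the section 8.1.1 primary endpoint

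*Protocol*

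**What the plan says.** The synopsis and section 8.1.1 define the primary composite in the same way. The early component is "one or more pregnancy loss(es) (either < 10 weeks gestation", with no condition on morphology. The later component is loss "beyond 10 weeks of gestation of a morphologically normal fetus documented by ultrasound or by direct examination of the fetus". The preterm component is "premature birth of a morphologically normal neonate before 34 weeks due to any of" pre-eclampsia, eclampsia or placental insufficiency.

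Section 4.1.1 gives a different primary endpoint, "one or more miscarriage (either < 10 weeks gestation or between 10 and 27+6 weeks gestation", plus early preterm birth and stillbirth, with no morphology condition on any part. Section 4.1.2, directly after it, restores the condition for the matching secondary endpoint: "Pregnancy loss > 10th week of gestation of a morphologically normal fetus documented by ultrasound or by direct examination of the fetus".

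Congenital abnormalities appear among the endpoints only inside secondary endpoint 8, "Neonatal morbidity (bleeding or thrombotic complications, infections, congenital abnormalities". Section 7.1 collects them after delivery, under the preterm-delivery and post-partum entries. Endpoint 12 covers safety in mother and neonate.

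On analysis, section 10.1 states that randomized women with outcome data are not excluded. On safety, section 9.2 makes a congenital anomaly a seriousness criterion but takes outcome-measure events out of the serious category. Section 9.2.1 exempts miscarriage after 10 weeks and stillbirth from serious adverse event reporting. At the second-trimester visit, section 7.1 records whether an anomaly scan took place. It names growth and Doppler as results to record, but not the anomaly finding. The protocol has no rule for termination of pregnancy.

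**The concern.** Treatment starts before conception, so fetal morphology is a post-randomization feature that the drug could in principle affect. Section 5.3 acknowledges that "hydroxychloroquine is labelled as 'contraindicated in pregnancy' according to the SmPC", and safety is a stated endpoint.

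Two things follow when a malformed pregnancy ends after 10 weeks without a live birth. First, the malformation comparison is restricted to babies who reach birth, which omits the cases severe enough to end the pregnancy. Second, under section 8.1.1 the woman stays in the denominator as a non-event, so any excess of such losses in one arm would slightly lower that arm's primary event rate. The first matters for interpreting safety. The second is a matter of direction more than size.

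**Working it through.** **1. How one case is scored.** Take a fetus with a major malformation that dies at 21 weeks.

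| Rule | Result |
|---|---|
| Synopsis and 8.1.1, loss before 10 weeks | not met (too late) |
| Synopsis and 8.1.1, loss after 10 weeks | not met (fetus not normal) |
| Synopsis and 8.1.1, birth before 34 weeks | not met (no normal neonate) |
| 10.1, analysis set | stays in, so a non-event |
| 4.1.1, miscarriage from 10 to 27+6 weeks | met, so an event |
| Endpoint 8, neonatal morbidity | not counted (no neonate) |
| Endpoint 12, safety | fetus not named |
| 9.2 and 9.2.1, serious adverse event | unclear |

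The last row is unclear because a congenital anomaly is a seriousness criterion, while miscarriage after 10 weeks is exempt whatever the morphology. Two neighbouring cases differ. A malformed fetus lost before 10 weeks is a primary event under both definitions. A malformed baby born alive before 34 weeks is a non-event under 8.1.1 but does enter endpoint 8.

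**2. The plan's own figure.** Section 10.2 gives 328 for 63% versus 47%, alpha 0.05 (two-sided assumed) and power 80%. The continuity-corrected formula gives 163 per arm, 326 in total. Without the correction it is 302, or 334 to 336 with 5% one-way crossover. The sample size is not in question. I take 164 per arm below (1:1 assumed).

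**3. Malformations missed by endpoint 8.** The documents give no malformation rate or share ending before birth. Assume 2-3% of pregnancies malformed and 10-50% of those ending before birth.
- Malformed: 328 × 0.02 = 6.6 to 328 × 0.03 = 9.8.
- Missed: 6.6 × 0.1 = 0.7 to 9.8 × 0.5 = 4.9, so about 1 to 5 fetuses.

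**4. An illustrative excess.** Assume 5% versus 2.5% malformed, with 30% ending before birth in each arm.
- True counts: 164 × 0.05 = 8.2 and 164 × 0.025 = 4.1.
- Seen by endpoint 8: 8.2 × 0.7 = 5.7 and 4.1 × 0.7 = 2.9. The ratio stays at 2.0, and the absolute excess falls from 4.1 to 2.9.
- Not seen: 8.2 × 0.3 = 2.5 and 4.1 × 0.3 = 1.2.
- Net imbalance on the primary endpoint: 2.46 − 1.23 = 1.23 women, and 1.23 / 164 = 0.75 points.
- Events displaced, if 63% of these women would otherwise have had an event: 1.23 × 0.63 = 0.8 women, or about 0.5 points.

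**5. Effect on the primary comparison with no true benefit.** Let m be the excess share of active-arm pregnancies lost this way, and take a base rate of 63%. Scored as non-events, the active-arm rate is 0.63 × (1 − m). Scored as events, it is 0.63 × (1 − m) + m. The one-sided chance of a false benefit under the non-event rule is 1 − Φ(1.96 − 0.63m / √(2 × 0.63 × 0.37 / 164)).

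| m (assumed) | Risk ratio, non-event | Risk ratio, event | False benefit |
|---|---|---|---|
| 0 | 1 | 1 | 2.5% |
| 0.5% | 0.995 | 1.003 | 2.9% |
| 1% | 0.990 | 1.006 | 3.3% |
| 3% | 0.970 | 1.018 | 5.4% |
| 5% | 0.950 | 1.029 | 8.6% |

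The net imbalance in step 4 corresponds to m = 0.75%, between the second and third rows. These values are upper-end, because 63% includes losses before 10 weeks and the event rate among pregnancies that pass 10 weeks is lower.

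**The case against.** The normal-morphology condition is deliberate. The composite is meant to capture outcomes related to antiphospholipid antibodies, and the glossary's definition of the syndrome uses the same condition. Section 5.3 reports no increase in malformations with hydroxychloroquine in the literature it reviews. Absence from endpoint 8 is not absence from safety reporting: section 9.2 lists congenital anomaly as serious, and section 9.2.1 requires adverse events outside its exemptions to be reported. Scoring of terminations and extra sensitivity analyses are often left to the statistical analysis plan.

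Much of this stands. The disease-specific primary endpoint is defensible and need not change, and a sensitivity analysis could be placed in the analysis plan. What does not stand is reliance on serious adverse event reporting as the backstop. Congenital abnormality is itself part of a secondary endpoint, so the outcome-measure exemption can be read to cover it, and the exemptions for later miscarriage and stillbirth carry no morphology condition. Nor can a later analysis plan recover an anomaly finding that the forms were not specified to collect.

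A reader might infer that every lost or terminated malformed pregnancy is a primary success. The documents do not support this. Losses before 10 weeks count whatever the morphology, section 4.1.1 counts spontaneous losses to 27+6 weeks, and non-event status for a termination is only the natural reading of silence.

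**Conclusion.** The point holds in a limited form. Under the synopsis and section 8.1.1, loss of a malformed fetus after 10 weeks is a primary non-event and falls outside the malformation endpoint. Section 4.1.1 contradicts the first of these. The main consequence is an incomplete malformation count, by about 1 to 5 fetuses under the assumed 2-3% prevalence and 10-50% ending before birth, with serious adverse event capture uncertain.

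A reader might also infer that a teratogenic effect could manufacture a benefit on the primary endpoint. The direction is right but the size does not bear it out: about 1.2 women of 164 net under the assumed doubling of malformations, and fewer in events displaced, against a 16-point design difference. The documents report no increased malformation risk. All malformation rates here are assumptions. The change is worth making because it is cheap and closes a gap in a stated safety question, not because the primary result is in danger.

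**What to change.** 1. Define a separate safety endpoint: any congenital abnormality in a live birth, stillbirth, loss or termination, as a proportion of all pregnancies.
2. Add a field for the anomaly finding to the adverse-pregnancy-outcome form, since section 7.1 specifies only that a scan took place.
3. Reconcile section 4.1.1 with the synopsis and section 8.1.1, and state how terminations are scored before and after 10 weeks.
4. Keep the disease-specific primary endpoint, and add one sensitivity analysis that counts losses at or beyond 10 weeks and births before 34 weeks for the listed causes regardless of morphology.

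The cost is endpoint wording, one form field and one extra analysis. The malformation count may look slightly less favourable than a count restricted to neonates.

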8.1.2 Secondary Efficacy Parameters

The secondary efficacy parameters will include the absence of the secondary endpoints as outlined above.

8.2 Procedures for Assessing Efficacy Parameters

The primary outcome of the HYPATIA study will be a composite of pregnancy complications as defined above (see primary and secondary outcomes).

Adverse pregnancy outcomes are defined under 'Glossary and Definition' (Section 2). Each adverse pregnancy outcome will be recorded for each individual case. Fetal growth will be assessed by using standardized ultrasound methods. Pre-eclampsia will be diagnosed according to international criteria (see definition in section 2), information with regards to the baby, i.e. gestational age at delivery, birth weight, mode of delivery, Apgar < 7 at 5 min, neonatal morbidity (bleeding or thrombotic complications, infections, congenital abnormalities), number of days in hospital and thrombotic events in the mother during the puerperium. Patients will be consented to give the trial team access to their child's hospital notes if needed (i.e. in case of admission to paediatric special care units or complications such as intraventricular haemorrhage).

Symptoms suggestive of VTE will be evaluated according to the usual diagnostic methods. Patients who present with symptoms suggestive of stroke, myocardial infarction or arterial thrombosis at other sites, generally present as a clinical emergency and clinical and diagnostic information will be obtained retrospectively from the center at which they have been managed.

Efficacy makers are defined as follows:

Miscarriage: The presence of a miscarriage will be determined due to standard medical practice at each participating unit. Usually this will include a history from the patient and at some centers ultrasound for confirmation.

Fetal death: This will be determined by ultrasound according to standard medical practice.

Intrauterine growth restriction: Serial ultrasound assessments according to standard medical practice and the use of growth percentiles will be used to determine the presence or absence of fetal growth restriction (individualized birth weight according to Gardosi).

Placental abruption: Patient history and ultrasound according to standard medical practice.

Premature birth: Birth between 24+0 and 36+6 weeks gestation.

Pre-eclampsia as defined in international guidelines [4]: Hypertension developing after 20 weeks gestation and the coexistence of one or more of the following new onset conditions:

1. Proteinuria (spot urine protein/creatinine >30 mg/mmol [0.3 mg/mg] or >300 mg/day or at least 1 g/L ['2 + '] on dipstick testing)

2. Other maternal organ dysfunction:

- renal insufficiency (creatinine >90 umol/L)
- liver involvement (elevated transaminases and/or severe right upper quadrant or epigastric pain)
- neurological complications (examples include eclampsia, altered mental status, blindness, stroke, or more commonly hyperreflexia when accompanied by clonus, severe headaches when accompanied by hyperreflexia, persistent visual scotomata)

• haematological complications (thrombocytopenia, DIC, haemolysis)

- 3. Uteroplacental dysfunction
 - fetal growth restriction

9 Assessment of Safety

9.1 Specification, Timing and Recording of Safety Parameters.

The trial visit schedule will enable face-to-face contact with patients to discuss any concerns and to address any possible adverse events or side effects. Adverse events will be followed up until resolution.

Patients will be advised to contact their respective research team to report any concerns about the treatment between trial visits. All babies will be having an eye and ear test within 6 weeks post-partum.

Patients with APS planning for pregnancy or pregnant are seen with a close follow up. For pregnant patients with APS the usual scheduled visits at St Thomas' Hospital, London are once every month, however, this practice may vary amongst centers. For the purpose of the HYPATIA study, we will expect all participating centers to adopt a similar approach.

Trial visits will be scheduled to coincide with routine follow up appointments and trial participation will not necessarily entail more frequent visits.

At each routine specialist follow-up clinic visit, routine clinical assessment will include assessment with regard to potential medication side effects. A blood test full blood count, kidney and liver function and a physical exam to ensure no potential adverse effects of hydroxychloroquine will be performed every three months as long as the patient is taking the IMP. These blood tests will be performed on the day of the usual visit, which means patients do not have to come to extra hospital appointments.

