	Selected centres: bloods for additional research Record whether patient has had anomaly scan, record fetal growth and uterine artery Doppler results (results can be recorded at 2 nd or 3 rd trimester visit). Record FGR.
Smoking status	 Smoking status update
US growth scans	Depending on the individual patient one or more US scans have been performed during the second trimester. All available growth scan results will be recorded. Information will be obtained from maternity records.
Medication	 All medications will be recorded. Compliance check (Kit number to be noted, date of current kit started & ended, number of tablets taken, number of tablets missed) IMP dispensation The patient will be asked to bring unused trial medication and empty packaging to each visit (number of tablets taken & number of tablets missed will be recorded), this will be collected, and a new supply will be given. All medications will be recorded. Compliance will be verified. The patient will be asked to bring unused trial medication and empty packaging to each visit, this will be collected, and a new supply given every 3 month.
Adverse events & Adverse pregnancy events	Enquiry about adverse events including adverse pregnancy events. In case the patient has miscarried an 'adverse pregnancy events' form has to be filled out (not SAE).

PREGNANCY follow up visit 3 3 rd Trimester visit (Gestational week 27 – end of pregnancy)	
US growth scans	Depending on the individual patient one or more US scans have been performed so far. All available growth scan results will be recorded. Information will be obtained from maternity records. If uterine artery Doppler results have not been documented at previous visit, they should be recorded.

Adverse events & Adverse pregnancy events	Enquiry about adverse events including adverse pregnancy events. In case the patient has miscarried an 'adverse pregnancy events' form has to be filled out (not SAE).
Medication	 All medications will be recorded. Compliance check (Kit number to be noted, date of current kit started & ended, number of tablets taken, number of tablets missed) IMP dispensation
	The patient will be asked to bring unused trial medication and empty packaging to each visit (number of tablets taken & number of tablets missed will be recorded), this will be collected and a new supply will be given.

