9.2.1 Adverse events that do not require reporting

Pregnancy itself is well known to potentially causing nausea and tiredness due to several physiological adjustments of the body especially in the first trimester. Any symptoms thought to be related to the physiological changes in pregnancy do not require reporting.

In patients with aPL we expect pregnancy complications. Therefore, aPL related pregnancy complications, such as miscarriage < 10 weeks gestation, miscarriage > weeks 10, premature birth < 34 weeks due to pre-eclampsia, eclampsia or FGR and stillbirth shall not be reported as SAE. For these events we have designed a special section in the electronic database 'adverse pregnancy outcomes', which shall be completed in this case. Any other adverse events will be reported.

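### Losses beyond 10 weeks need documented normal morphology, which the trial's procedures do not secure, and no rule says how a loss with unknown morphology is scored

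*Protocol*

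**What the plan says.** Endpoint. Section 8.1.1 and the synopsis include in the composite a loss "beyond 10 weeks of gestation of a morphologically normal fetus documented by ultrasound or by direct examination of the fetus". A loss before 10 weeks carries no morphology condition. Success is the reverse of the composite: "The primary efficacy parameters will include the absence of pregnancy complications".

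Section 4.1.1 defines the same composite differently. It counts miscarriage "either < 10 weeks gestation or between 10 and 27+6 weeks gestation" and sets no condition on morphology. Section 4.1.2 then lists the late-loss component with the condition, although 4.1.1 says that the secondary endpoints present the components of the primary.

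Ascertainment. For miscarriage, section 8.2 relies on standard practice at each unit: "Usually this will include a history from the patient and at some centers ultrasound for confirmation". The next entry reads "Fetal death: This will be determined by ultrasound according to standard medical practice". The word miscarriage is not confined to early losses, because section 9.2.1 speaks of complications "such as miscarriage < 10 weeks gestation, miscarriage > weeks 10".

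Schedule and data items. The first-trimester visit (section 7.1, to 13+6 weeks) lists no scan. In the flowchart (section 4.3), growth scans start in the second trimester, and the only scan with a stated gestational window is the uterine artery Doppler at 20–24 weeks. The second-trimester visit says: "Record whether patient has had anomaly scan, record fetal growth and uterine artery Doppler results". Growth and Doppler are asked for as results, the anomaly scan only as done or not done.

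**The concern.** The endpoint demands a piece of evidence that the measurement procedures do not guarantee. A patient's history can establish that a pregnancy was lost, but not that the fetus was morphologically normal. Under the literal wording of 8.1.1, a loss shortly before 10 weeks known from history alone is a primary event, and the same loss shortly after 10 weeks is not. Whether a woman with a late loss counts as a success would then depend on whether her centre scanned or examined the fetus.

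At stake are primary events that disappear for want of documentation, not because the fetus was abnormal. Late loss is one of the components with the largest contrast in the protocol's own retrospective cohort (section 3: 2% with HCQ, 11% without), so losing these events would shrink the difference on which the trial is powered.

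**Working it through.** **1. Reproduce the stated sample size.** Inputs from section 10.2: 63% vs 47%, alpha 0.05 (taken as two-sided), power 80%, 5% crossover, total 328. Allocation of 1:1 is assumed because no ratio is stated.

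- n per arm = (1.960 + 0.842)² × [0.63×0.37 + 0.47×0.53] / 0.16² = 7.849 × 0.4822 / 0.0256 = 147.84, or 295.7 in total.
- Crossover: 295.7 / 0.95² = 327.6, which rounds up to 328.

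The stated size reproduces and is not in question.

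**2. Baseline power with 164 per arm.** Pooled standard error under the null, unpooled under the alternative:

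- SE0 = √(2 × 0.55 × 0.45 / 164) = 0.0549; SE1 = √(0.4822 / 164) = 0.0542.
- Power = Φ[(0.16 − 1.96 × 0.0549) / 0.0542] = 83.3%. With 5% one-way dilution of the effect it is 79.4%.

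**3. Score a share f of late losses as non-events.** The protocol gives no value for f, so the range is an assumption. The control rate becomes 0.63 − f × 0.11 and the HCQ rate 0.47 − f × L, where L is the late-loss rate on HCQ. Two values of L are used: 2%, as in the retrospective cohort, and 8.2%, the rate if late losses fall in the same ratio as the composite (11% × 47/63). The same power formula is applied, without dilution.

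| f | Rates, L = 2% | Power | Rates, L = 8.2% | Power |
|---|---|---|---|---|
| 0 | 63.0% vs 47.0% | 83.3% | 63.0% vs 47.0% | 83.3% |
| 10% | 61.9% vs 46.8% | 78.7% | 61.9% vs 46.2% | 81.8% |
| 25% | 60.3% vs 46.5% | 70.6% | 60.3% vs 45.0% | 79.5% |
| 50% | 57.5% vs 46.0% | 55.0% | 57.5% vs 42.9% | 75.6% |
| 100% (bound) | 52.0% vs 45.0% | 24.4% | 52.0% vs 38.8% | 67.2% |

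With 5% one-way dilution, the figures at 25% are 66.1% and 75.3%, and at 50% they are 50.8% and 71.2%.

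**4. Treat such losses as missing and drop them instead (L = 2%).**

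- f = 25%: control 0.6025/0.9725 = 62.0% of 159.5 women; HCQ 0.465/0.995 = 46.7% of 163.2 women; power about 79%.
- f = 50%: control 0.575/0.945 = 60.8% of 155.0 women; HCQ 0.46/0.99 = 46.5% of 162.4 women; power about 73%.

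**5. Limits of the arithmetic.** The subtraction treats late losses as separate from the other components. In the retrospective cohort the late-loss gap (11 − 2 = 9 points) and the placental-complication gap (10.9 − 2 = 8.9 points) already sum to 17.9, more than the whole 16-point difference before any early losses. Strict additivity is therefore doubtful, and the L = 2% column is best read as the pessimistic end.

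**The case against.** A reader might infer that the protocol scores true late losses as successes. It does not say so. Nothing states whether a late loss with unknown morphology is an event, a non-event or missing, and section 10.1 has a missing-data framework (missing at random in the main analysis, with a not-at-random sensitivity analysis) into which such cases might be put. This stands, and the point is limited to what the literal wording would do. The missing-data route would be a poor answer, however. Only a woman who has lost a pregnancy can lack this item, so missingness depends directly on the outcome, and step 4 shows that power still falls.

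The ultrasound rule for fetal death in section 8.2 may be the natural match for losses beyond 10 weeks. That is fair, but ultrasound can confirm death without showing morphology, and the separate miscarriage rule can also reach these losses.

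A reader might also infer that the anomaly-scan result is never captured. That goes too far. Flowchart footnote 9 says that all scans belong on the eCRF. It is attached to the Doppler row, but its wording is general. Section 9.2.1 describes a database section for adverse pregnancy outcomes whose fields are not shown, so a morphology field may already exist. Routine-care scans will exist for many women, and direct examination of the fetus is an accepted alternative. What remains is that no listed procedure or visit item secures the morphology finding.

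The morphology condition mirrors the APS definition in the glossary, so counting unknowns as events gives up some specificity for aPL-related loss. This is a real trade-off, and the sensitivity analysis below is meant to show it.

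Finally, bias between arms might be suspected. The trial is double blind and minimised by centre, so under-documentation should affect both arms alike.

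**Conclusion.** The mismatch stands. The synopsis and 8.1.1 require evidence of normal morphology, the procedures in 7.1 and 8.2 do not ensure that it exists, 4.1.1 omits the requirement, and no rule covers a loss with unknown morphology. This is more than detail left to a later plan, because the endpoint wording, taken as written, would let a woman with a late pregnancy loss count as a success according to local scanning practice.

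The consequence is mainly fewer events and less power, varying by centre. If undocumented late losses are scored as non-events, power falls from about 83% to 71–80% at an assumed 25% undocumented and to 55–76% at 50%. These ranges rest on the assumed shares, on a late-loss rate of 11% in controls taken from one retrospective cohort, on HCQ rates of 2% to 8.2%, and on late losses being separate from other events. The documents do not support a single figure, nor a claim that the sample size of 328 is wrong.

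**What to change.** 1. Reconcile section 4.1.1 with 8.1.1 and the synopsis so that there is one definition of the late-loss component.
2. State that a loss beyond 10 weeks is a primary event unless a morphological abnormality is documented. Report the version limited to documented normal morphology as a sensitivity analysis.
3. Make sure that the adverse pregnancy outcomes form records morphology (normal, abnormal, not documented) and its source, and that the anomaly-scan result is recorded as well as the fact of the scan.

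Cost: an amendment to the endpoint wording, made before unblinding because births have already occurred (section 5.3), and at most a few eCRF fields completed from existing records, including retrospectively for losses already reported. No additional scans or visits are needed. The downside is that a few losses of fetuses with an undetected abnormality will count as events in both arms.
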